9.6 Randomization

The department of biometry of the SZB will generate a randomization algorithm according to their SOPs. The randomization procedures will be carried out stratified by site and smoking status (smoker vs non-smoker) via permuted blocks within each stratum. Allocation to treatments will be done in a 1:1 ratio:

Treatment group A (Verum): 120 subjects

Treatment group B (Placebo): 120 subjects

The unblinded randomization list with the allocation of randomization numbers to treatments is kept confidential with department of biometry of the SZB. The derived site-specific randomization list is forwarded only to unblinded study personnel of the study site (refer to 10.8 and 10.12).

The allocation of a subject (Subject-ID) to a treatment is done by the randomization number as provided on the randomization list. After screening, the assignment of the randomization number to a Subject ID happens in consecutive order (i.e. “first-come-first-serve” approach).

Subjects who meet all eligibility criteria will be treated starting on Visit 1 (Day 1, during or immediately after surgery) either with Verum (Treatment A) or with Placebo (Treatment B).

Details are described in an IMP Manual.

9.7 Time of inclusion into clinical study

A patient is enrolled into the clinical trial after having signed the informed consent.

A patient is included in the clinical trial after having received a randomization number.

10 Investigational Medicinal Product (IMP)

10.1 General

Study drug includes both Investigational [Medicinal] Product (IP/ IMP) and Non-investigational [Medicinal] Product (Non-IP/Non-IMP) and can consist of the following:

- All products, active or placebo, being tested or used as a comparator in a clinical trial
- Study required premedication, and
- Other drugs administered as part of the study that are critical to claims of efficacy (e.g., background therapy, rescue medications)
- Diagnostic agents: (such as glucose for glucose challenge) given as part of the protocol requirements must also be included in the dosing data collection

10.2 Specification of IMP and auxiliary Medicinal Products (AxIMP)

IMP 1: Nicotinell 14mg/24-Stunden-Pflaster

Product name	Nicotinell 14mg/24-Stunden-Pflaster
Name of manufacturer	GlaxoSmithKline Consumer Healthcare GmbH & Co.KG
Substance name (if applicable, give substance code)	Nicotine
Name and dose of active ingredient per unit	14mg/24h
Other ingredients	Refer to SmPC
Pharmaceutical form	Transdermal patch
Mode of administration	transdermal
Batch number	Not yet available
Storage conditions	Not above 25°C
Expiry date	Not yet available
Mode of action	transdermal
Interactions	No interactions with other drugs are known

IMP 2: Placebo

Product name	Patchinga Freestyle Libre 3
Name of manufacturer	Shanghai Ruiquan Medical Equipment Co., Ltd.
Substance name (if applicable, give substance code)	Not applicable
Name and dose of active ingredient per unit	None
Other ingredients	Not applicable
Pharmaceutical form	Patch
Mode of administration	topical
Batch number	Not yet available

Confidential

EU trial No: 2023-503349-71-00/ TransNiDeG

Attachment 001 to SOP MW-009.001

Clinical Trial Protocol version 2.0 of 28-JUN-2023

Version 001

Effective Date: 18-Mai-2022

Storage conditions	No special requirements
Expiry date	Not yet available
Mode of action	Not applicable
Interactions	Not applicable
If necessary; additional information concerning toxicology, preclinical results, pharmacodynamics, pharmacokinetics	

The batch number / expiry date for IMP will be provided with the batch records in the Trial Master File.

No auxiliary IMPs will be applied in this clinical trial.

10.3 Authorization Statement

The IMPs are products with a marketing authorization in Germany.

Nicotinell 14mg/24-Stunden-Pflaster will be used in accordance with the marketing authorization with the exception that also non-smokers will be applied.

The Placebo patch is manufactured in accordance with ISO 13485:2016 and fulfills all legal requirements as per MDR 745/2017.

10.4 Side Effects

A summary of the most important side effects and contraindications which are reported in the corresponding Summary of Product Characteristic(s) (Fachinformation) for Nicotinell 14mg/24-Stunden-Pflaster is presented below:

Nicotine can cause headaches, dizziness and nausea, increase in heart rate and temporary mild increases in blood pressure. However, when using Nicotinell 14 mg / 24-hour patch, the level of nicotine in the blood remains largely the same and there are no levels are reached as after smoking a cigarette. Therefore, such side effects are unlikely to occur during treatment with Nicotinell 14 mg / 24-hour patch are much less pronounced.

Very frequent (> 10%) side effects:

- Headache
- Cold- and flu-like symptoms

Frequent (1-10%) side effects:

- Dizziness
- Agitation
- Feeling of fear
- Nervousness
- Concentration disturbance
- Sleeplessness
- Tiredness
- Abnormal dreams

Confidential

EU trial No: 2023-503349-71-00/ TransNiDeG

Attachment 001 to SOP MW-009.001

Clinical Trial Protocol version 2.0 of 28-JUN-2023

Effective Date: 18-Mai-2022

Version 001

Page 33 of 69

- Change in blood pressure
- Cough
- Nausea
- Stomach pain
- Gastrointestinal disorder
- Skin reaction at the application site (e.g. burning feeling, swelling, redness, itching). Most of these reactions were of mild nature and resolved within 48 hours. In severe cases redness and swelling continued for 1-3 weeks. Significant skin reactions occurred after 3-8 weeks after start of treatment.
- Muscle pain
- Movement disorders

Occasionally (0.1 – 1%) side effects:

- Sleepiness
- Emotional lability
- Irritability
- Depressive mood
- Confusion
- Memory disorder
- Paresthesia
- Taste disorder
- Visual disorder
- Palpitation
- Heat waves
- upper respiratory tract Infection
- vomiting
- obstipation
- diarrhea
- flatulence
- abnormal stool
- dry mouth
- gingivitis
- Stomach ulcer
- Increased sweating
- Acne
- Joint pain
- Muscle cramps
- Back pain
- Swallowing disorder
- Thyroid disorder
- Painful lymph nodes
- Cystitis
- Weakness
- Pain

Confidential

EU trial No: 2023-503349-71-00/ TransNiDeG

Attachment 001 to SOP MW-009.001

Clinical Trial Protocol version 2.0 of 28-JUN-2023

Effective Date: 18-Mai-2022

Version 001

Page 34 of 69

- Malaise
- migraine

Rare side effects (0.01 – 0.1%):

- Tremor
- Pain in the chest
- Breathing difficulties
- Cardiac arrhythmia
- Skin reaction at the application site like skin (hyper-)pigmentation, vasculitis

10.5 Packaging and Labelling of IMP

The IMPs (both, Verum and Placebo patches) will be ordered and supplied either by the local pharmacies or by the local purchase department of the study sites.

Nicotinell patches will be supplied as packages containing 7 patches in their authorized packaging with no modifications. Pursuant to Directive EU 536/2014 Art. 67 No. 2, a trial-specific label will be placed on the outer packaging in order to ensure subject safety and reliability and robustness of clinical trial data.

Placebo patches will be supplied as packages containing 25 patches. Subject-individual sets with 7 patches each will be assembled by the unblinded members of the investigator's team. These sets will be labelled with a trial-specific label, too.

Labelling will be done by the local pharmacy of the study site or by a pharmacy with a respective manufacturing authorization.

Details are described in the IMP manual.

10.6 Transport of IMP

Since IMP is ordered and supplied by local pharmacies, no transport is necessary.

10.7 Storage requirements of IMP

The IMP(s) must be stored under the following conditions:

IMP 1 (Nicotinell patch): below 25°C

IMP 2 (Placebo patch): no special storage requirements

The investigator will be responsible for ensuring the correct storage and sufficient stocks of the IMP(s) at the site. The investigator bears the responsibility for the proper storage in a secure location at the site, preferably in a lockable cabinet. **Access to the IMPs has to be restricted only to unblinded members of the investigator's team.** It has to be paid special attention that **study personnel who is applying and covering the IMP is not involved in any other trial-specific procedures.**

Personnel who have access to the IMPs need to be listed (name and responsibilities) on the Authorization and Delegation Log in the trial specific Investigator Site File (ISF). The investigator has to ensure that the IMP is only used according to the protocol.

10.8 Dosage, Mode of Application and Dose Schedule of IMP

IMP patches will be applied by unblinded members of the investigator's team only.

Application on Day 1 will be done during or immediately after surgery. Application on Days 2 to 7 should be done preferably in the morning with an interval of approximately 24h (+/-6h) between treatments.

The dose of 14mg/24h for Nicotine patches was chosen as the medium dose for Nicotine patches being used for smoking cessation. This dose was proven safe even in non-smokers with only transient nausea as the only symptom [55] and in the elderly, where no serious adverse events were noted [63]. Also in critically-ill patients, a dosing of 14mg/24h was tolerated without relevant side-effects [61]. The dose was chosen to have most likely a significant effect without causing harm to the subjects.

According to the SmPC, the patch has to be placed either on the upper arm, upper hip or in the shoulder area. For standardization purposes in this study, the patches will be applied on the upper arm.

The patch should be placed on non-injured, clean and dry skin with as less hair as possible. The patch will be left on the application area for approximately 24 hours (+/-6h) after which the patch will be replaced by a new one. The application area has to be changed every day to avoid skin reactions. Therefore, it is preferred to change the arm for application every day.

After application of the Verum or Placebo patch, another patch has to be placed over the IMP patch to cover it for blinding purposes. This "blinding patch" has to cover the IMP patch totally. It has to be ensured that any manipulation of the "blinding patch" can be discovered.

Both patches (the IMP patch and the "blinding patch") must not be taken off during the time of application e.g. for taking a shower. Although the IMP patch is not water-resistant, it can be left on the skin when showering carefully.

The application and blinding process is described in detail in the IMP Manual.

10.9 Handling of IMP at the Site and Drug Accountability

Every trial site maintains records to document receipt of the IMP, the stocks of IMP, the dispense and use by the individual subject, the reconciliation, and the return of unused investigational medicinal products and their disposal on appropriate forms (e.g. drug dispensing log, drug accountability log).

Verification of (blinded) IMP accountability will be part of on-site monitoring activity. It is the responsibility of the investigator or the monitor (whoever first discovers it) to inform the sponsor delegated person/ Coordinating Investigator in case of deficiency regarding e.g. storage or accountability of the IMP.

Copies of all forms completed at the trial site will be returned to the sponsor delegated person/Coordinating Investigator at the end of the trial upon request or will be collected by the monitor during the close out visit.

Confidential

EU trial No: 2023-503349-71-00/ TransNiDeG

Attachment 001 to SOP MW-009.001

Clinical Trial Protocol version 2.0 of 28-JUN-2023

Version 001

Effective Date: 18-Mai-2022

IMP must only be applied to subjects who have signed the informed consent and who have been included in the trial. The dispensing of IMP to subjects outside of this clinical trial is not permitted.

Further details about receipt, storage, handling, dispensing are given in the IMP-Manual.

10.10 Subject/ Treatment Compliance

The IMP will be applied by an unblinded authorized member of the investigator's team. Prior to every IMP application, the unblinded study team member will check the blinding patch and the underlying IMP patch of the former day for manipulation and detachment. IMP application and any deviations will be documented.

Treatment compliance will be determined via verification of the drug accountability after database lock (i.e. unblinding) by the Study Monitor.

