10.11 Return and Disposal of IMP

All unused IMP will be destroyed at the trial site by the responsible Study Monitor according to SZB SOP. In case of destruction, a destruction form has to be completed with the information about date and location of destruction, sort and amount of IMP.

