10.13 Unblinding

Unblinding may be performed by the trial site using Emergency Codes which are provided to the trial site by the SZB as sealed Emergency Envelopes. These envelopes have to be stored at a location known and accessible to all study personnel. All study personnel have to be specifically trained. Integrity of envelopes is controlled by the Study Monitor.

The investigator should adhere to the randomization procedure of the clinical trial and ensure that the code is only broken according to the protocol.

As a matter of principle, unblinding is only performed after the closing of the database for the final analysis.

However, premature unblinding of a subject subject may be necessary in order not to jeopardise his/her safety (ICH-GCP 5.13.4):

- In emergency situations, if it is necessary for the subject subject's safety, i.e. if the further treatment depends on the knowledge of the investigational medicinal product.
- In the event of accidental administration of the investigational medicinal product to a person who is not a clinical trial subject.
- In the event of the death of a subject, if a causal relationship between the treatment with the investigational medicinal product and death is suspected.

- In the event of SAEs/SUSARs, under certain conditions (causal relationship with the investigational medicinal product).

In emergency situations or in the event of accidental administration of the investigational medicinal product, the decision whether unblinding is necessary lies with the investigator. If possible, the sponsor delegated person/Coordinating Investigator should be consulted first. Date and time of unblinding, name of the person who has broken the blind have to be documented on the respective emergency envelope. Any broken emergency envelope has to be filed in the Investigator Site File (ISF).

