10.14.1 Prohibitions

As a rule, a subject should abstain from smoking during the 7 days of treatment with the IMP. In case a subject deviates from this rule, this should be documented in the patient file and in the eCRF.

It will be discussed in the Data Review Meeting together with the Coordinating Investigator and Biometrician whether the subject will be excluded from the analysis or not.

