14.2.4 Definition of Populations Included in the Analysis

This clinical trial will be analysed according to the intention-to-treat (ITT) principle. This means that the subjects will be analysed in the treatment arms to which they were randomised, irrespective of the occurrence of any intercurrent events (e.g. whether they refused or discontinued the treatment or whether other protocol violations are revealed).

The per-protocol (PP) population is a subset of the ITT population and is defined as the group of subjects who had no major protocol violations, received a predefined minimum dose of the treatment and underwent the examinations required for the assessment of the endpoints at relevant, predefined times i.e. representing a hypothetical population without intercurrent events and adhering to the protocol. The analysis of the PP group will be performed for the purpose of a sensitivity analysis.

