14.2.7 Protocol Violations

Protocol violations are major deviations from the procedures outlined in this document including but not limited to:

- missed evaluations
- incorrect timing of evaluations
- relevant non-compliance with investigational medicinal product, if applicable
- the intake of medications not allowed
- smoking during the IMP treatment phase
- any non-adherence to the protocol that would have an impact to the subject's rights, safety or welfare and or reliability and robustness of study data

After a subject has been enrolled, it is the investigator's responsibility to make a reasonable effort to correct any protocol violations and to continue the subject's participation in the trial, if possible.

Protocol violations do not constitute a justification for withdrawal of a subject from the trial themselves.

Protocol violations will be reported to the sponsor/sponsor delegated person during the course of the trial in the monitoring reports and the clinical study report.

All protocol violations will be listed and the impact on the evaluation of the subjects concerned will be discussed prior to statistical analysis.

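### Section 10.10 determines treatment compliance after database lock and unblinding, although per-protocol membership depends on it and nothing requires that set to be fixed blind

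*Protocol*

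**What the plan says.** Protocol section 10.10 sets the time, method and person for compliance: "Treatment compliance will be determined via verification of the drug accountability after database lock (i.e. unblinding) by the Study Monitor". Section 10.13 is consistent with lock coming first, since "unblinding is only performed after the closing of the database for the final analysis".

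Two other sections use compliance as an input. Section 14.2.4 admits to the PP set only subjects who, among other conditions, "received a predefined minimum dose of the treatment". Section 14.2.7 lists as a protocol violation "relevant non-compliance with investigational medicinal product, if applicable", and subjects with major violations are left out of the PP set.

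On the timing of these decisions, section 14.2.7 says that all violations are listed and that "the impact on the evaluation of the subjects concerned will be discussed prior to statistical analysis". Section 10.14.1 sends cases of smoking during treatment to a data review meeting, which decides "whether the subject will be excluded from the analysis or not". It does not say when that meeting takes place.

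Section 10.10 also states that the unblinded team member checks the previous day's patch for manipulation and detachment before each new application, and that "IMP application and any deviations will be documented". Section 10.9 provides for blinded verification of accountability during on-site monitoring.

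**The concern.** A PP set is useful as a sensitivity analysis only if its members were chosen without knowledge of treatment. Here the protocol names a determination of compliance that becomes available after lock, and it describes that moment as unblinding. By then the DGE grades are final as well. Whoever decides whether a subject received enough treatment, or whether non-compliance was relevant, could know both the arm and the outcome.

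The PP analysis is the protocol's check on how far the primary comparison depends on adherence. If its membership is open to that knowledge, neither agreement nor disagreement between the PP and ITT results can be read with confidence. This is a sequence that the protocol states, so it is not a detail left for the SAP. An SAP that fixed the PP set in a blinded review would have to use a compliance determination other than the one section 10.10 prescribes.

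**Working it through.** The plan gives no figure to reproduce, and the point is one of order, so the check sets the sections side by side.

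| Step | Source | Timing stated |
|---|---|---|
| Each application and deviation documented | 10.10 | As it happens, during the 7 treatment days |
| Accountability checked blind | 10.9 | During on-site monitoring |
| Violations reported to the sponsor | 14.2.7 | During the trial |
| SAP finalised | 14, introduction | Before lock and unblinding |
| Database closed, then unblinding | 10.13 | After the last patient |
| Treatment compliance determined | 10.10 | After lock, equated with unblinding |
| Impact of violations discussed | 14.2.7 | Before the analysis; relation to lock not stated |
| Data review meeting | 10.14.1 | Not stated |
| PP membership fixed | 14.2.4 | Not stated |

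1. PP membership needs the dose received (14.2.4) and a judgement on relevant non-compliance (14.2.7).
2. The protocol's named determination of compliance comes after lock and unblinding (10.10).
3. A decision that uses this determination cannot come before it. The dose and non-compliance parts of PP membership therefore fall after unblinding.
4. The timing rule in 14.2.7 does not prevent this. A discussion held after unblinding but before the models are run still satisfies it.
5. Finalising the SAP before unblinding can fix the dose threshold blind. It does not settle which subjects meet the threshold, nor which non-compliance is relevant or which violations are major.
6. The first three rows of the table show that the information for a blind decision is collected during the trial. The protocol does not say that these records, rather than the verification after lock, decide compliance.

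Step 3 is an inference from 10.10 and 14.2.4 read together. The protocol never says outright that PP membership is assigned after unblinding.

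**The case against.** The best defence is that section 10.10 describes a closing verification by the monitor and not the assignment of analysis sets. Applications are recorded daily, accountability is checked blind, violations are reported during the trial, and a data review meeting exists. The minimum dose is to be set in advance, and the SAP is final before unblinding. A numerical threshold applied to contemporaneous patch records leaves little room for choice, even after lock.

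Much of this stands. It shows that a blind decision is feasible and that discretion over the dose criterion may be small. It does not change the order stated in 10.10, and it leaves open the judgement on relevant non-compliance and major violations.

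A reader might infer stronger points that the documents do not support:

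- **That the PP set cannot be fixed blind.** The daily application records and the blinded accountability checks contradict this.
- **That compliance rests on counting leftover packs.** Section 10.9 defines the accountability records as also covering use by the individual subject.
- **That the monitor is unblinded by destroying stock.** Section 10.11 says "All unused IMP will be destroyed at the trial site by the responsible Study Monitor" but gives no time for it. Sections 10.9 and 10.10 have the monitor check accountability blind during the trial and verify it after lock. Early unblinding by this route is therefore not shown.
- **That the bias can be sized.** Suppose, purely as an assumption, that 5 nicotine patients with DGE were dropped from 120 per arm at 50% DGE. The odds ratio for any DGE would move from (60/60)/(60/60) = 1.00 to (55/60)/(60/60) = 0.917, and ln(0.917) = -0.087. That is 0.087/0.42 = 0.21, about one fifth of the precision figure of 0.42 in section 14.2.3. The example takes every exclusion from one arm and one outcome, and it uses a dichotomised endpoint. It is not an estimate for this trial.

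**Conclusion.** The point holds as an error of stated sequence with limited reach. Followed literally, section 10.10 places compliance-based PP decisions after treatment is known, and no other section requires the PP set to be fixed earlier.

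Only the PP sensitivity analysis is affected. The main analysis is by ITT and does not use compliance, so the primary odds ratio, the 240 planned subjects and the precision target do not change. No numerical size can be attached, because the protocol gives neither the threshold nor an expected rate of non-compliance. Trained staff apply every patch, so the number of subjects concerned may be small.

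The conclusion assumes that the determination in 10.10 is the one meant to feed 14.2.4 and 14.2.7. The protocol names no other. If the SAP already fixes PP membership blind from the application records, the remaining fault is that section 10.10 contradicts it and needs rewording.

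**What to change.** - **Section 10.10:** determine compliance from the daily application and deviation record already required, that is, the number of patches applied (0 to 7) and any detachments. Enter these in the eCRF without treatment identity, and support them with the blinded accountability checks of section 10.9.
- **Sections 14.2.4 and 14.2.7:** state that PP membership, including the judgement on relevant non-compliance and major violations, is fixed and signed at a blinded data review before database lock and unblinding.
- **Section 10.14.1:** say that its data review meeting is this same blinded review.
- **Accountability check after lock:** keep it as confirmatory only, and report any discrepancy without changing the PP list.

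The cost is wording in a few sections and a small eCRF entry. The underlying record is already made. No dose, schedule or clinical rule changes, and the size of the minimum dose remains for the sponsor to set.
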